Glaucoma is the leading cause of irreversible blindness worldwide, with Asia accounting for 60% of the estimated number of people with glaucoma (64.3 million) in 2013.¹ In China alone, there are nearly 10 million cases, suggesting a strong need for public health strategies to alleviate this important health issue.^{2,3}

Current glaucoma treatment strategies involve reducing or lowering a patient's elevated intraocular pressure, with the most effective approaches employing either eye drops, laser therapy, or surgery. Additionally, glaucoma treatment requires long-term follow-up care, making patient compliance central to a successful regimen.⁴ However, the treatment of glaucoma in low-resource settings presents significant issues, as the disease is typically asymptomatic until substantial, irreversible vision loss has already occurred.⁵ Poor adherence to follow-up^{6,7} and misconceptions in rural China about glaucoma as a symptomatic disease makes topical medicine an unlikely sustainable option for treatment.⁵

Yet, surgery as the primary treatment modality for glaucoma in rural China come with its own set of challenges. It has been well documented that vision after glaucoma surgery declines initially, with the majority of cases resolving over 1-6 weeks.⁸ Concerns about dis-satisfaction with vision may lead to negative attitudes towards surgery in the community, and affect uptake of not only glaucoma surgery, but also other eye operations, particularly cataract, the leading cause of global blindness, and which can only be treated surgically. Rural community acceptance of surgery is of particular importance because sources of knowledge about glaucoma primarily come from friends, relatives and the news, but not physicians.⁵

Traditionally, the preoperative procedure for glaucoma surgery entails a comprehensive discussion between the physician and patient about the role of surgery, but it is unclear how effective these sessions are at disseminating information.^{9,10} Of primary concern is the extent to which patients comprehend the purpose of glaucoma surgery as a mechanism to prevent future vision loss, rather than recover lost vision. This problem is particularly acute in rural Chinese settings, where patient loads are heavy, and time for detailed discussions may be limited. The situation is further complicated by limited knowledge among caregivers in many cases, and well-documented lack of trust between physicians and patients in rural China.¹¹

Educational interventions employing videos to assist in the preoperative informed consent process have shown visual aids to be a promising tool for increasing patient comprehension and satisfaction.^{12,13,14} Even more essential is the repetition of information in improving patient understanding.¹²

For this study, we will evaluate the effectiveness of repeated showings of an educational video has in raising patient satisfaction with glaucoma surgery.

Objectives

Overall Objective: This study will assess whether an educational video is effective in increasing patient satisfaction with glaucoma surgery.

1. Investigate the impact of educational interventions on glaucoma patients' surgical satisfaction.
2. Investigate the post-operative satisfaction of rural glaucoma patients in county hospitals
3. Investigate the difference in postoperative satisfaction between urban and rural glaucoma patients in urban hospitals
4. Investigate other factors that influence postoperative glaucoma satisfaction.

Methodology

Study Design: Randomized controlled trial of an educational intervention.

Study Population: Patients scheduled to undergo glaucoma surgery at either the Wenzhou Eye Hospital or at four rural county-level hospitals in Guangdong province.

Since there may be existing differences in baseline glaucoma surgery satisfaction levels due to patients' place of residence and choice of hospital, we will divide our study population into the following three groups:

- **Group 1:** Urban patients seeking glaucoma surgical treatment at an urban hospital.
- **Group 2:** Rural patients seeking glaucoma surgical treatment at an urban hospital.
- **Group 3:** Rural patients seeking glaucoma surgical treatment at a rural or county-level hospital.

Recruited patients from Wenzhou Eye Hospital will be separated into Groups 1 and 2 based off place of residence. Recruited patients from the Guangdong CREST county-level hospitals will be enrolled into Group 3. Each of these groups will be randomized separately (stratified randomisation) to ensure a balance across study groups with regard to this characteristic.

Sample Size Calculations: 264 total patients

Patient Enrolment Criteria:

- Glaucoma patients \geq 18 years of age undergoing trabeculotomy or iridotomy

Patient Exclusion Criteria:

- VA $<$ 20/400 (0.05)
- Patients who had previously undergone trabeculotomy
- Severe mental disabilities preventing participants from completing a self-administered questionnaire

Intervention: Subjects will be asked to watch a 5-10 min education film two times (pre-op one day and post-op one day).

Control: Standard patient procedure that includes a pre-operative discussion with an ophthalmologist about glaucoma surgery, during which the surgeon gains the patient's informed consent. Subjects will not be asked to watch education film.

Outcomes

Main outcome: The mean satisfaction outcome over two follow-up visits (1 day and 1 week).

Composite outcome, in which multiple end points are combined, are frequently used as primary outcome measures in randomized trials and are often associated with increased statistical efficiency. (Freemantle N, Calvert M, Wood J, Eastaugh J, Griffin C. Composite outcomes in randomized trials: greater precision but with greater uncertainty? *JAMA*. 2003; 289: 2554-2559)

While our satisfaction questionnaire has not been previously validated, it contains several items from the Glaust questionnaire, a validated questionnaire measuring patient satisfaction with glaucoma treatment. (Ruiz, M. A., Pardo, A., Martinez de la Casa, J. M., Polo, V., Esquiro, J., & Soto, J. (2010). Development of a specific questionnaire measuring patient satisfaction with glaucoma treatment: Glausat. *Ophthalmic epidemiology*, 17(3), 131-143.)

Secondary outcomes:

2. The rate of willingness to recommend surgery to a friend or relative with glaucoma
Measurement method: Satisfaction questionnaire

3. Personality in both groups using Eysenck Personality Questionnaire-Revised Short Scale for Chinese (EPQ-RSC) to assess glaucoma patients' personality. This test measures four aspects of an individual's personality traits: extraversion, neuroticism, presence of psychoticism (aggressiveness or hostility), and lie (tendency to conform).

4. Knowledge scores about glaucoma.

5. Intraocular pressure in both groups. Unit of Intraocular pressure is mmHg.

6. Visual acuity in both groups

Visual acuity testing use Snellen-based letter charts, such as a Snellen score of 6/12 (20/40), indicating an observer can resolve details as small 2 minutes of visual angle, corresponds to a LogMAR of 0.3 (since the base-10 logarithm of 2 is 0.3)

Informed Consent

Informed consent to participate in an educational intervention will be obtained. A standard consent form will be employed and will indicate that, as part of an educational randomized control trial, some of the participants will receive free consultations with a health professional. If they are unable to read it, the form will be read to them in Chinese. Afterwards, they will be invited to sign.

Participant Withdrawal

Patients in either the intervention or control group are free to leave the study at any time. Data collected up to the point of withdrawal of consent will be anonymized, securely stored, and be included in data analysis.

Randomisation

Pre-randomization baseline assessment

Following consent, baseline patient satisfaction levels with previous glaucoma treatment and medical care will be evaluated. Patients will be categorized as “urban” or “rural” based off their place of residence and separated into their designated groups based off place of residence and hospital.

Randomization: Patients will be randomized based off clinic week. For example, all patients having surgery one week will watch the video and be placed in the intervention group. The following week, all patients will be placed in the control week.

Baseline data:

- Patient
 - Age/Sex
 - Profession
 - Martial Status
 - Long-term Residence
 - Distance from home to hospital
 - Time from home to hospital
 - Current glaucoma treatment
 - Baseline uncorrected and best-corrected visual acuity in operative eye
 - Intraocular pressure in operative eye

The Intervention

Subjects will be asked to watch a 5-10 min education film. These sessions will occur during their pre-operative and post-operative 1 day visit.

The film follows the journey of an elderly patient scheduled to undergo glaucoma surgery, beginning with a face-to-face Q&A health session with an eye doctor. After surgery, the patient talks about his post-operative eyesight and discusses the benefits of early diagnosis and glaucoma surgery for treatment with his community.

Participant Recruitment Timeline

An administrator will schedule a time for patients to come in for surgery. When patients come for their pre-surgery visitation, they will be approached for study recruitment. After signing the informed consent form denoting their voluntary participation into the study, they will fill out three questionnaires: 1) Personality (EPQ-RSC) 2) Knowledge of glaucoma treatment.

Based off their identity as an “urban” or “rural” patient, they will be separated accordingly into the different groups. Randomization will be determined by clinic week.

The timetable displays what questionnaires will be filled out at each visitation for the control and intervention group.

	Control Group	Intervention Group
Pre-Surgery Visitation	1. Informed consent 2. Personality (EPQ-RSC) 3. Knowledge of glaucoma treatment 4. Baseline Satisfaction questionnaire	5. Informed consent 6. Personality (EPQ-RSC) 7. Knowledge of glaucoma treatment 8. Baseline satisfaction questionnaire 9. Video
Surgery		
Post-surgery Day 1	1. Satisfaction questionnaire	1. Satisfaction questionnaire 2. Video
Post-surgery Week 1	1. Satisfaction questionnaire 2. Knowledge of glaucoma treatment	1. Satisfaction questionnaire 2. Knowledge of glaucoma treatment

Analyses

Statistical Analysis

- Mean patient satisfaction grade for cumulative scores from 2 satisfaction questionnaires, comparing intervention and control groups, with and without adjustment for baseline patient factors.

Prevention of Bias

Potential Harms and Benefits of the Study

Potential Harms

There are no clinical harms from the study protocol itself, as the intervention group is solely receiving additional health counseling sessions.

Potential Benefits

The patients in the intervention group will receive additional counseling with a health professional, which may deepen their understanding of glaucoma surgery

Literature Cited

1. Tham, Y. C., Li, X., Wong, T. Y., Quigley, H. A., Aung, T., & Cheng, C. Y. (2014). Global prevalence of glaucoma and projections of glaucoma burden through 2040: a systematic review and meta-analysis. *Ophthalmology*, 121(11), 2081-2090.
2. Foster, P. J., & Johnson, G. J. (2001). Glaucoma in China: how big is the problem? *British Journal of Ophthalmology*, 85(11), 1277-1282.
3. Wong, T. Y., Loon, S. C., & Saw, S. M. (2006). The epidemiology of age-related eye diseases in Asia. *British Journal of Ophthalmology*, 90(4), 506-511.
4. Budenz, D. L. (2009). A clinician's guide to the assessment and management of nonadherence in glaucoma. *Ophthalmology*, 116(11), S43-S47.

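### Allocation is by clinic week, with only alternation illustrated and no random sequence or concealment described, and it conflicts with separate randomisation of the two Wenzhou groups

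*Combined protocol and SAP*

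**What the plan says.** Study Population (Methodology) defines three groups: urban patients at Wenzhou (Group 1), rural patients at Wenzhou (Group 2) and rural patients at county hospitals (Group 3). The stated reason is that "there may be existing differences in baseline glaucoma surgery satisfaction levels" by residence and choice of hospital. It then says: "Each of these groups will be randomized separately (stratified randomisation) to ensure a balance across study groups with regard to this characteristic".

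The Randomisation section makes the clinic week the unit of allocation. Its illustration is: "For example, all patients having surgery one week will watch the video and be placed in the intervention group". It continues: "The following week, all patients will be placed in the control week". Participant Recruitment Timeline says that, once classified as urban or rural, "they will be separated accordingly into the different groups", and immediately afterwards that "Randomization will be determined by clinic week".

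The same section gives the order of events. An administrator books surgery, the patient is approached at the pre-surgery visit, and consent and questionnaires follow. Baseline satisfaction sits under the heading "Pre-randomization baseline assessment": "Following consent, baseline patient satisfaction levels with previous glaucoma treatment and medical care will be evaluated".

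Nothing says how a sequence of weeks is generated, who holds it or when it is released. The Prevention of Bias heading has no text in the copy read, which may be an artefact of that copy.

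The Executive Summary says influencing factors are adjusted for in all analyses. Statistical Analysis plans the comparison of means both with and without adjustment, and names no term for clinic week.

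**The concern.** There are two defects.

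First, the only rule shown is alternation. If it is followed, the arm is fixed when the surgery date is set, before the assessment that the protocol calls pre-randomisation. Anyone who knows the calendar could then affect who is booked into, or invited in, a video week, even without intent. The outcome is self-reported satisfaction, so a difference in who enrols would read as an effect of the film. Adjustment reaches only measured factors.

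Second, two sections describe different designs. If every patient operated on in a week gets the same arm, Groups 1 and 2 are not randomised separately, and balance by residence is not ensured. The plan itself expects baseline satisfaction to differ by residence.

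As written, a reader cannot tell whether individuals within groups, random weeks or alternating weeks are allocated.

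**Working it through.** **The text**

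- *Unit.* Study Population implies allocation within each of three groups. The Randomisation section puts all patients of a week in one arm. Groups 1 and 2 share a hospital, so a common weekly arm means one sequence for both. Group 3 is at other hospitals and could have its own sequence, so the conflict is confined to Groups 1 and 2.
- *Timing.* Booking, then approach, then consent, then baseline. Under alternation the arm is determined at booking.

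**Size of the selection problem (illustration)**

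The only design figure in the documents is the total of 264. No shift size, SD, arm size, week size or intracluster correlation (ICC) is given. Assumed: 264/2 = 132 per arm, SD 1, two-sided 5%, no true effect.

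SE = √(2/132) = 0.1231. For a selection shift b between arms, the rejection rate is Φ(−1.96 + b/SE) + Φ(−1.96 − b/SE).

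| Shift b (SD) | Unadjusted, no clustering |
|---|---|
| 0.05 | 6.9% |
| 0.10 | 12.8% |
| 0.20 | 36.9% |

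A shift of 0.10 SD corresponds to 0.10 × 132 ≈ 13 patients in one arm who differ by 1 SD from those otherwise enrolled. If adjustment removed half of it (assumed, same SE), b falls to 0.05 and the rate from 12.8% to 6.9%.

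**Adding week clustering**

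Design effect = 1 + (m − 1) × ICC. With m = 3 and ICC 0.01 it is 1.02, and SE = 0.1231 × √1.02 = 0.1243. With m = 5 and ICC 0.05 it is 1.20, and SE = 0.1348. Week sizes and ICCs are assumed.

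| Analysis | Shift | Design effect 1.02 | Design effect 1.20 |
|---|---|---|---|
| Cluster-aware | 0.10 SD | 12.7% | 11.5% |
| Clustering ignored | 0 | 5.2% | 7.4% |
| Clustering ignored | 0.10 SD | 13.1% | 15.3% |

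The rows that ignore clustering use the naive critical value 1.96 × 0.1231 with the larger true SE. A simulated t-test on week means (40,000 runs) agrees with the cluster-aware row: 12.5% with 88 weeks and 11.0% with 52 weeks at b = 0.10, and 5.1% and 4.9% at b = 0. A cluster analysis therefore corrects the standard error but does not remove selection.

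**Precision under week allocation**

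The effect detectable with 80% power from 264 independent patients is (1.96 + 0.842) × 0.1231 = 0.345 SD.

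- Effective total: 264/1.02 = 259; 264/1.20 = 220.
- Power at 0.345 SD: 79.2% and 72.5%.
- Total that restores the precision: 264 × 1.02 = 269.3, so 270; 264 × 1.20 = 316.8, so 317.
- Hospital-weeks: 264/3 = 88; 264/5 ≈ 53.

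Over a wider assumed range (3 to 10 patients per week, ICC 0.01 to 0.10) the design effect reaches 1.90, the effective total 139 and power 53%.

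**The case against.** The strongest reply has four parts.

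1. *Alternation is only an example.* A random order of weeks is not excluded, and the documents do not say who knows the calendar. This stands: the text shows an unspecified method and an inconsistency, not that selection has occurred. It does not rescue the plan, because the method still cannot be identified.
2. *The sections could be compatible.* Participant Recruitment Timeline separates patients into groups just before saying that clinic week decides, so each group might have its own calendar. That reading is possible, but it sits badly with an illustration that covers all patients operated on in a week.
3. *The magnitudes are assumed, and the largest are unadjusted.* This is correct. Residence and baseline satisfaction are collected, and adjustment for them could remove part of a shift. The defects in the text do not depend on these rates.
4. *Keeping the clinic week leaves some predictability, whereas individual randomisation conceals fully and keeps the planned stratification.* This also stands. Once a week's first patient is told the arm, staff know it; with 3 to 5 patients per week, that covers two-thirds to four-fifths of patients if they are invited one after another. Preferring week allocation is a judgement about contamination, which the documents do not discuss.

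The empty Prevention of Bias heading might have held missing detail. That would not undo the illustrated alternation or the conflict over Groups 1 and 2.

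**Conclusion.** The concern holds and must be fixed. Allocation is by clinic week, alternation is the only rule illustrated, and neither sequence generation nor concealment is described. Under the illustrated rule the arm is knowable before enrolment. On the natural reading, the weekly rule contradicts separate randomisation of Groups 1 and 2.

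The size of any bias cannot be derived from the documents. On the assumed inputs, modest selection of 0.05 to 0.20 SD takes a nominal 5% test to between 6.9% and 36.9% without adjustment. Ignoring week clustering alone gives 5.2% to 7.4%. Confidence in the textual finding is high; the rates are illustrations only.

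**What to change.** **Recommended: keep the clinic week and make it random and concealed.**

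- Generate a random order of weeks by computer for each hospital, with varied block sizes (for example 4 and 6), held away from the scheduler and recruiters.
- Release a week's arm as late as the workflow allows, where possible after its surgical list has closed. The documents do not say when lists close. If a list is still open when the first pre-operative film is due, release then, flag patients added later, and run a sensitivity analysis without them.
- Tell each patient the arm only after consent and baseline. Invite all consecutive eligible patients and log those not enrolled, by week.
- Analyse the mean of the day-1 and week-1 scores with week as the cluster, for example a mixed model with a random hospital-week effect and small-sample degrees of freedom. Adjust for hospital, urban or rural residence (which varies only at Wenzhou) and baseline satisfaction.
- Replace the separate-randomisation sentence in Study Population with a statement that weeks are randomised within hospital and residence is handled by adjustment.

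**Alternative, if the sponsor accepts possible contamination between patients:** randomise individuals within Groups 1, 2 and 3 from a concealed list opened after consent and baseline. Change the Randomisation and Participant Recruitment Timeline sections to match. The Study Population sentence then stays and the week-cluster analysis does not apply.

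**Cost.** A short amendment, a computer-generated list and a screening log. The precision loss shown above belongs to the week design already in the plan; the amendment makes it visible. The recommended route gives up balance by residence through design. Some guessing also remains: someone who knows the block sizes and all past weeks would be right about 67% to 69% of the time (simulated), against every week after the first under alternation. Under the alternative, if controls received 10% of the film's effect (assumed), power at 0.345 SD would fall from 80% to 71%.
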